6.3.1.12. IgG Concentrations Against Prefusion F Measured at Birth

- Analysis set: Evaluable immunogenicity – infant ([Section 4](#)).
- Analysis methodology: Descriptive summary statistics. Results obtained from out-of-window blood draws will also be removed. Missing serology results will not be imputed, as MCAR is assumed.
- GMCs of the IgG against prefusion F subgroup A and subgroup B, and combined RSV A/B, at birth will be presented. For each vaccine group, n, GMC, and 95% CI will be presented.

6.3.1.13. MA-RTI, MA-LRTI, and Severe MA-LRTI Due to RSV Occurring 0 to 730 Days After Birth in Premature Infants <37 Weeks of Age

- Analysis set: Evaluable efficacy – infant ([Section 4](#)).
- Analysis methodology: VE will be analyzed using a conditional exact test based on the binomial distribution of the number of disease cases in the RSV vaccine group, given the total number of cases in both groups. Results obtained after the infant received palivizumab or another monoclonal antibody targeting RSV or after he/she had transfusions of more than 20 mL/kg of any blood products at ≤ 180 days of age will be excluded.
- For each group, the number (n), percentage, and 95% CI of MA-RTI, MA-LRTI and severe MA-LRTI due to RSV cases occurring within 0 to 730 days after birth will be presented for each group.
- VE compared to placebo along with the 95% CI will be presented for each analysis interval separately.

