2.1.3. Exploratory Objectives

2.1.3.1. Exploratory Objectives – Infant Participants

- To evaluate the efficacy of RSVpreF in reducing the incidence of MA-RTI due to RSV.
- To evaluate the efficacy of RSVpreF in reducing the incidence of MA-RTI.
- To evaluate the efficacy of RSVpreF in reducing the incidence of MA-LRTI due to RSV in infants after 12 months of age.
- To evaluate the efficacy of RSVpreF in reducing the incidence of severe MA-LRTI due to RSV in infants after 6 months of age.
- To evaluate the efficacy of RSVpreF in reducing the incidence of hospitalization due to RSV in infants after 6 months of age.
- To evaluate the efficacy of RSVpreF in reducing the incidence of all-cause MA-LRTI in infants after 6 months of age.

- To evaluate the efficacy of RSVpreF in reducing the incidence of MA-LRTIs due to RSV A and the incidence of MA-LRTIs due to RSV B.
- To describe the non-RSV infectious etiology of MA-RTI in the study population.
- To evaluate RSV serum neutralizing titers elicited by RSVpreF and transferred transplacentally.
- To assess the impact of RSVpreF on RSV illness based on socioeconomic factors.
- To assess the effect of RSVpreF on healthcare utilization.
- To describe the efficacy of RSVpreF in reducing the incidence of MA-RTI, MA-LRTI, and severe MA-LRTI in premature infants <37 weeks of age.

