2.2. Study Design

This is a Phase 3, multicenter, randomized, double-blinded, placebo-controlled study to assess the efficacy, safety, and immunogenicity of bivalent RSVpreF or placebo (1:1 randomization) in infants born to healthy women vaccinated during pregnancy, and the safety and immunogenicity in the pregnant women. This will be a global study, including sites in both the northern and southern hemispheres, and it will span multiple RSV seasons.

This is an event-driven study with a target of 124 adjudicated (primary-endpoint) cases of MA-LRTI due to RSV (meeting the case definition in the per-protocol infant population described in [Section 9.2 of the protocol](#)). Vaccination of maternal participants will occur at a time of year such that the infant is likely to be exposed to seasonal RSV during the first 6 months of life. It was anticipated that approximately 6900 mother-infant pairs would be needed to accumulate 124 per-protocol cases prior to the global COVID-19 pandemic. With the variable RSV season, the sample size may need to be increased and enrollment could go up to 10,000 maternal participants based on the number of RSV cases.

Study-eligible pregnant women will be randomized in a 1:1 ratio to receive a single dose RSVpreF or placebo. The dose of RSV prefusion F antigen in RSVpreF for this study will be 120 µg (60 µg A and 60 µg B).

Assessments for mothers will include parameters to allow descriptions of safety, tolerability, and immunogenicity of the vaccine in maternal participants.

For all infant participants, data will be collected for any medically attended respiratory illness to assess for cases of LRTI due to RSV (efficacy endpoint). Additionally, throughout the study all respiratory illnesses, SAEs, and NDCMCs reported will be assessed in this population. Infant participants enrolled during the first year of the study will be followed up for 24 months after birth, to include longer-term RTI surveillance and safety oversight to address safety and the possibility of conferred enhanced protection (antibody persistence) during a second RSV season. All other infants will be followed up for 12 months after birth. All MA-RTIs meeting the protocol definition for a potential study endpoint will be adjudicated by an independent EAC. In addition, this study will use an E-DMC to monitor vaccine safety and efficacy and study futility.

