4. ANALYSIS SETS (POPULATIONS FOR ANALYSIS)

Data for all participants will be assessed to determine if participants meet the criteria for inclusion in each analysis population prior to unblinding and releasing the database and classifications will be documented per standard operating procedures.

Population	Description
Enrolled	All participants who sign the informed consent document.
Randomly assigned to investigational product	All maternal participants who are assigned a randomization number in the IRT system.
Evaluable efficacy – infant (per-protocol)	All infant participants who are born to maternal participants who did not have major protocol deviations prior to the delivery and who received the investigational product to which they were randomized at least 14 days prior to delivery, are eligible, and have no major protocol deviations.
ITT efficacy – infant	All infant participants who are born to vaccinated maternal participants.
Evaluable immunogenicity – infant	All infant participants who are born to maternal participants who did not have major protocol deviations prior to the delivery and who received the investigational product to which they were randomized, are eligible, have blood drawn for assay testing within the specified time frame, ^a have valid and determinate assay results for the proposed analysis, and have no major protocol deviations.
Evaluable immunogenicity – maternal	All maternal participants who are eligible, receive the investigational product to which they were randomized, have blood drawn for assay testing within the specified time frame, ^b have valid and determinate assay results for the proposed analysis, and have no major protocol deviations.
ITT immunogenicity – infant	All infant participants who are born to vaccinated maternal participants and have at least 1 valid and determinate assay result for the proposed analysis.
ITT immunogenicity – maternal	All randomized maternal participants who receive investigational product and have at least 1 valid and determinate assay result for the proposed analysis.
Safety – infant	All infant participants who are born to vaccinated maternal participants.
Safety – maternal	All randomized maternal participants who receive investigational product.

- a. A cord blood sample must be obtained on the day of birth. If cord blood is unavailable, a venous blood sample may be collected from the infant preferably within 24 hours but up to 7 days after birth.

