5.2.1. Analyses for Binary Endpoints

The number and percentage of participants in each category will be summarized. The 95% CI for percentage, and for the difference in percentages, will also be presented, where appropriate.

The analysis of efficacy will use a conditional exact test¹ based on the binomial distribution of the number of disease cases in the RSV vaccine group, given the total number of cases in both groups. The number of cases $x_i \sim P(\lambda_i)$, where $P()$ is the Poisson distribution ($i = 1$ denotes placebo, $i = 2$ denotes vaccine). It is known that $x_2|T = t \sim B(T, \pi)$, where $B()$ is the binomial distribution, $T = x_1 + x_2$ (the total number of events), and $\pi = \lambda_2 / (\lambda_1 + \lambda_2)$. Then, assuming equal numbers of participants per group, testing the hypothesis $H_0: VE \leq \theta$ is equivalent to testing $H_0: \pi \geq (1 - \theta) / (2 - \theta)$.

The 95% CI for proportions will be constructed by the Clopper-Pearson method described by Newcombe.² The 95% CI will be presented in terms of percentage.

The 95% CI for differences in the proportions will be computed using the Miettinen and Nurminen method.³ The 95% CI will be presented in terms of percentage.

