6.1.1.1.1. Main Analysis

- Estimand strategy: Hypothetical.
- Analysis set: Evaluable efficacy – infant ([Section 4](#)).
- Analysis methodology: VE will be analyzed using a conditional exact test based on the binomial distribution of the number of disease cases in the RSV vaccine group, given the total number of cases in both groups.
- Intercurrent events and missing data: All postdiscontinuation or postviolation observations will be censored; such events include the infant receiving palivizumab or another monoclonal antibody targeting RSV and the infant receiving transfusions of more than 20 mL/kg of any blood products at ≤ 180 days of age.
- For each group, the number (n), percentage, and 95% CI of RSV-positive MA-LRTI cases occurring within 90 days, 120 days, 150 days, and 180 days after birth, as confirmed by the EAC, will be presented for each group. Severe MA-LRTI cases are a subset of MA-LRTI cases, and all severe MA-LRTI cases will also be considered MA-LRTI cases.

- VE compared to placebo along with the corresponding 100(1- alpha)% CI (adjusted for the interim) will be presented. This will be based on raw numbers of cases and also with an adjustment for any differences in follow-up time. See [Section 5.1](#) for testing procedures.
- Kaplan-Meier curves showing accrual of cases for this endpoint over 180 days will be presented.

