6.4. Subset Analyses

[Table 10](#) summarizes the defined subgroup analyses. Additional subset analyses (not defined here) may also be performed if deemed necessary. Immunogenicity testing may be performed on subsets of participants if needed prior to testing on all study participants and may be reported separately.

Table 10. Subgroup Analysis for Infant Participants

Subgroup	Endpoints	Population
GA at the time of vaccination (≥ 24 to < 28 weeks, ≥ 28 to < 32 weeks, ≥ 32 to ≤ 36 weeks)	
 Primary efficacy endpoints Immunogenicity endpoints Hospitalization due to RSV (up to 730 days) 	
 Evaluable efficacy – infant Evaluable immunogenicity – infant Evaluable efficacy – infant
Time from vaccination to delivery		
≤ 14 Days > 14 Days and ≤ 30 days > 30 Days	
 Immunogenicity endpoints 	
 ITT immunogenicity – maternal/infant
Country	
 Primary efficacy endpoints Immunogenicity endpoints Pregnancy & birth outcome Hospitalization due to RSV (up to 730 days) 	
 Evaluable efficacy – infant Evaluable immunogenicity – infant Safety – maternal/infant Evaluable efficacy – infant
Country subcategories (level of income) ⁴	
 Primary efficacy endpoints Immunogenicity endpoints Pregnancy & birth outcome Hospitalization due to RSV (up to 730 days) 	
 Evaluable efficacy – infant Evaluable immunogenicity – infant Safety – maternal/infant Evaluable efficacy – infant
Demographic risk factors		
Breastfeeding (exclusivity and duration)	
 Primary and secondary efficacy endpoints 	
 Evaluable efficacy – infant
Maternal smoking (smoker [current]/nonsmoker)	
 Primary and secondary efficacy endpoints 	
 Evaluable efficacy – infant
Number of household members	
 Primary and secondary efficacy endpoints 	
 Evaluable efficacy – infant
Infants who received palivizumab (yes/no)	
 Primary and secondary efficacy endpoints 	
 ITT efficacy – infant

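### SAP 6.3.1.13 estimates VE in premature infants with a case-count test that assumes equal group sizes, although group size and follow-up in this subset are settled after vaccination

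*SAP*

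**What the plan says.** Section 6.3.1.13 covers RSV-related MA-RTI, MA-LRTI and severe MA-LRTI from 0 to 730 days after birth in premature infants of the evaluable efficacy set. Its method is that "VE will be analyzed using a conditional exact test based on the binomial distribution of the number of disease cases", and its output is that "VE compared to placebo along with the 95% CI will be presented for each analysis interval separately". It also presents the number, percentage and 95% CI of cases per group.

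The test is defined in section 5.2.1. Given T total cases, the vaccine-group count is binomial with probability π, and a hypothesis on VE is converted to one on π "assuming equal numbers of participants per group".

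For the primary endpoints (6.1.1.1.1 and 6.1.1.2.1) the plan adds of VE: "This will be based on raw numbers of cases and also with an adjustment for any differences in follow-up time". Sections 6.2.1.1.1 and 6.2.1.3.1 say the same for secondary endpoints. Section 6.3.1.13 has no such sentence.

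On design, section 2.2 states: "Study-eligible pregnant women will be randomized in a 1:1 ratio to receive a single dose RSVpreF or placebo". It also plans 24 months of follow-up for infants enrolled in the first year and 12 months for the rest. Section 4 limits the evaluable efficacy set to infants whose mothers "received the investigational product to which they were randomized at least 14 days prior to delivery".

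**The concern.** Equal group size is a fair working assumption for all infants in a 1:1 trial. It is weaker for a subset defined by gestational age at birth. Randomization acts on mothers before delivery. Prematurity, and delivery at least 14 days after vaccination, are known only later. Nothing in the design fixes the vaccine-to-placebo ratio of premature infants or of their person-time over 0 to 730 days.

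Without a term for group size, a difference in the number of premature infants is read as efficacy or as lack of it. The primary and secondary VE analyses have an adjusted version that would show this. The subset more exposed to unequal groups does not. It is also the only VE analysis that the SAP plans specifically for premature infants; Table 10 has no subgroup by gestational age at birth.

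**Working it through.** **1. What the method computes.** The SAP gives no figures for premature infants, so Table 11 serves to identify the formula. Take Clopper-Pearson limits for π = x2/T, where x2 and x1 are vaccine and placebo cases, and convert with

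VE = 1 - [π/(1 - π)]/R, R = N2/N1.

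Use R = 1 and the levels in the Table 11 footnote: half the 1-sided alpha of 0.014% or 0.15% in section 7.2 for the efficacy rows, and 95% for the futility rows.

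| Cases, vaccine v placebo | Table 11 | Recomputed, R = 1 |
|---|---|---|
| 6 v 37 | 84% (27, 98) | 83.8% (27.2, 98.3) |
| 14 v 48 | 71% (25, 91) | 70.8% (25.4, 90.5) |
| 24 v 19 | -26% (-145, 34) | -26.3% (-143.9, 33.7) |
| 29 v 33 | 12% (-49, 49) | 12.1% (-49.3, 48.5) |

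One limit is about a point off; the rest agree to rounding. The method as the SAP applies it is therefore VE = 1 - x2/x1, with no denominators.

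**2. Effect of unequal groups.** The expected ratio x2/x1 is about R(1 - VE), so unadjusted VE is about 1 - R(1 - VE).

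| True VE | R = 0.8 | R = 0.9 | R = 1.1 | R = 1.2 |
|---|---|---|---|---|
| 0% | 20% | 10% | -10% | -20% |
| 50% | 60% | 55% | 45% | 40% |

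**3. Effect on one observed split.** Assume 10 vaccine and 20 placebo cases.

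- SAP formula: 1 - 10/20 = 50.0% (-11.9, 79.1).
- R = 0.8: 1 - 0.5/0.8 = 37.5% (-39.9, 73.9).
- R = 1.2: 1 - 0.5/1.2 = 58.3% (6.7, 82.6).

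At R = 1.2 the corrected interval excludes 0 and the uncorrected one does not.

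**4. How far R can move by chance.** With n premature infants in total and no vaccine effect on prematurity, the SD of log R is about 2/√n, and the 95% range of R is exp(±1.96 × 2/√n). Subset sizes are assumptions; 345 and 690 are 5% and 10% of the 6900 pairs in section 2.2.

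| n | 95% range of R |
|---|---|
| 200 | 0.76 to 1.32 |
| 345 | 0.81 to 1.24 |
| 690 | 0.86 to 1.16 |

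**5. Whether chance imbalance inflates the error rate.** If vaccination affects neither prematurity nor disease, each case is equally likely to fall in either arm. Over randomizations x2 given T is then B(T, 0.5), whatever R turns out to be. With 40 cases the 1-sided rejection rate is 1.9%, below the nominal 2.5%. Conditional on a given R it does move: with 30 cases it is 7.8% at R = 0.8, 2.1% at R = 1 and 0.6% at R = 1.2. Those conditional rates average out unless R is shifted systematically.

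**The case against.** A reader might infer that any imbalance biases VE and inflates the false-positive rate. Step 5 shows that this does not follow. Chance variation in R is already inside the binomial variance. With 345 premature infants, R = 0.8 lies about 2.1 SD out (log 0.8 = -0.223; SD 2/√345 = 0.108). A systematic error needs a vaccine effect on prematurity or on entry to the evaluable set, and the SAP neither states nor quantifies one. This objection stands.

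A reader might also say that the plan ignores the number of premature infants altogether. It does not: section 6.3.1.13 reports percentages per group, and section 5.2 gives n and N for categorical summaries. An imbalance would be visible, and a risk ratio could be worked out from the output. The reported VE and its interval would still not reflect it.

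Nor does section 6.3.1.13 itself say that raw counts or equal groups are used. That reading rests on section 5.2.1 and on the missing adjustment sentence. It is an inference, but no other definition of the test is given.

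Extending the point to the Table 10 subgroups is not supported. Their efficacy rows largely concern primary and secondary endpoints, whose methods already include a follow-up-adjusted VE. Asking for 90- to 180-day windows in premature infants would be a preference, not the correction of an error.

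The stakes are low. The analysis is exploratory, sits outside the alpha-controlled families, and has a descriptive objective covering "severe MA-LRTI in premature infants <37 weeks of age". Case numbers may be small: at the planning rate of 124 cases per 6900 pairs, 345 infants would give 124/6900 × 345 ≈ 6 MA-LRTI cases, although longer follow-up, higher risk or the MA-RTI endpoint would raise this. In the 10 v 20 example, R = 0.8 moves VE by 12.5 points inside an interval 91 points wide.

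**Conclusion.** The point holds as a minor one. Read with section 5.2.1, section 6.3.1.13 gives a VE that is right for the infants observed only if the two premature groups have equal size and follow-up, which the design does not guarantee. The misstatement is about 10 points at a true VE of 50% for R = 0.8 or 1.2, and about 20 points at a true VE of 0%. R, the case counts and the subset sizes are all assumptions, so neither the size nor the direction in this trial can be known from the SAP.

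Chance imbalance costs precision and leaves the unconditional error rate intact. Systematic bias arises only if vaccination changes who enters the subset. In that case denominators remove the arithmetic part, but not the selection bias from conditioning on a postvaccination outcome.

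**What to change.** In section 6.3.1.13, define VE as 1 - (x2/N2)/(x1/N1), or the same with person-time in place of N. Take exact conditional limits from

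π = R(1 - θ)/(1 + R(1 - θ)),

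with R the observed vaccine/placebo ratio of premature infants at risk or of their person-time. At R = 1 this reduces to (1 - θ)/(2 - θ), the expression in section 5.2.1. Person-time also handles the mix of 12- and 24-month follow-up within 0 to 730 days.

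Add one sentence saying that this corrects for unequal group size or follow-up, but that the comparison still conditions on a postvaccination outcome and is open to selection bias.

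The cost is a few lines of SAP text and one extra parameter in existing code. No new data are needed, and the primary and secondary analyses are unchanged.

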6.3.2. Exploratory Endpoints: Maternal Participants

6.3.2.1. Incidence of All-Cause MA-RTIs From Vaccination Up to 180 Days After Delivery

- Analysis set: Safety – maternal ([Section 4](#)).
- Analysis methodology: Descriptive summary statistics for all-cause MA-RTI up to 180 days.
- For each group, the number (n), percentage, and 95% CI of MA-RTI all-cause cases occurring up to 180 days will be presented.

6.3.2.2. RSV A and RSV B Serum Neutralizing Titers Measured Before Vaccination and at Delivery Visit

6.3.2.2.1. Main Analysis

- Analysis set: Evaluable immunogenicity maternal ([Section 4](#)).
- Analysis methodology: Descriptive summary statistics. Results obtained from out-of-window blood draws will also be removed. Missing serology results will not be imputed, as MCAR is assumed.
- GMTs of the RSV A and RSV B serum neutralizing titers at each available time point will be descriptively summarized for each vaccine group, along with associated 2-sided 95% CIs.
- GMT of the combined RSV A/B serum neutralizing titer at each available time point will be descriptively summarized for each vaccine group, along with associated 2-sided 95% CIs.
- GMFRs and associated 2-sided 95% CIs will be provided for RSV A and RSV B serum neutralizing titers from before vaccination to each available time point after vaccination for each vaccine group.
- GMFR and associated 2-sided 95% CIs will be provided for the combined RSV A/B serum neutralizing titers from before vaccination to each available time point after vaccination for each vaccine group.
- GMRs of the RSV vaccine group to the placebo group for the RSV A and RSV B serum neutralizing titers at each available time point after vaccination will be calculated, along with associated 2-sided 95% CIs.
- GMR of the RSV vaccine group to the placebo group for the combined RSV A/B serum neutralizing titer at each available time point after vaccination will be calculated, along with associated 2-sided 95% CIs.

- RCDCs for RSV A and RSV B serum neutralizing titers for a combination of prespecified time points and vaccine groups will be generated.

6.3.2.2. Sensitivity Analysis

A sensitivity analysis will be performed to exclude immunogenicity data (RSV-neutralizing titers and IgG against prefusion F) from mothers following onset of RSV infection between vaccination and delivery (based on evidence from the nonvaccine-antigen assay).

6.3.2.2.3. Supplementary Analysis

The main analysis will also be performed based on the mITT immunogenicity maternal population. This analysis will be performed if there is at least 10% difference between the evaluable immunogenicity maternal population and mITT immunogenicity maternal population.

6.3.2.3. IgG Concentrations Against Prefusion F Measured Before Vaccination and at Delivery Visit

- Analysis set: Evaluable immunogenicity maternal ([Section 4](#)).
- Analysis methodology: Descriptive summary statistics. Results obtained from out-of-window blood draws will also be removed. Missing serology results will not be imputed, as MCAR is assumed.
- GMCs of IgG against prefusion F at each available time point by vaccine group. For each vaccine group, n, GMC, and 95% CI will be presented.
- GMFRs and associated 2-sided 95% CIs will be provided for IgG concentrations against prefusion F from before vaccination to each available time point after vaccination for each vaccine group.

6.3.2.4. Ig Concentrations Against Nonvaccine RSV Antigens Measured Before Vaccination and at Delivery Visit

All attributes (including analysis methodology and reporting results) for this endpoint will be similar to those stated in Section 6.3.2.3.

